UNIVERZITNÁ NEMOCNICA MARTIN
[name]
TRANSPLANTAČNO-NEFROLOGICKÉ ODDELENIE
TRANSPLANT-NEPHROLOGY DEPARTMENT

STUDY TITLE

A Randomized Controlled Study of Daratumumab for Microvascular Inflammation (MVI) in Kidney Transplant Recipients With or Without Donor-Specific Antibodies

(DARA-MVI)

NCT number:

In Martin, Slovakia 05th NOV 2025

Acronym

DARA-MVI Study (Daratumumab for Microvascular Inflammation in Kidney Transplantation)

Official Title

A Randomized Controlled Study of Daratumumab for Microvascular Inflammation (MVI) in Kidney Transplant Recipients With or Without Donor-Specific Antibodies

Brief Summary

The DARA-MVI Study is a prospective, randomized, controlled, open-label trial designed to evaluate the effect of daratumumab on microvascular inflammation (MVI) in kidney transplant recipients with C4d-negative biopsies. Participants with biopsy-proven MVI will be randomized to receive either daratumumab or observation with standard monitoring. The study will assess changes in histologic MVI score, donor-derived cell-free DNA (dd-cfDNA), donor-specific antibodies (DSA), and graft function over 12 months.

Study Design

Type: Interventional (Clinical Trial)

Allocation: Randomized (1:1 ratio)

Intervention Model: Parallel Assignment

Masking: Open-label (pathology and laboratory assessments blinded)

Primary Purpose: Treatment

Estimated Enrollment: 80 participants (40 per cohort)

Randomization: Block randomization (block size = 4) using MedCalc software
Duration: 12-month follow-up per participant

Arms and Interventions

Arm A – Observation: Participants with MVI, C4d-negative, and DSA-negative will undergo observation with standard monitoring. DSA and dd-cfDNA will be measured every 3 months for 12 months.

Arm B – Daratumumab: Daratumumab 1800 mg subcutaneously once monthly × 3 doses plus standard monitoring of DSA and dd-cfDNA every 3 months.

Control Group: Biopsy-negative, DSA-negative, dd-cfDNA-negative patients matched for time post-transplant and donor type.

Outcome Measures

Primary Outcome: Change in microvascular inflammation score (Banff g + ptc) between baseline and 12 months.

Secondary Outcomes:

1. Change in eGFR from baseline to 12 months.
2. Development of de novo DSA.
3. Change in dd-cfDNA (% and copies/mL).
4. Histologic resolution/progression of MVI.
5. Adverse events related to daratumumab.
6. Patient and graft survival at 12 months.

Eligibility Criteria

Inclusion: Age ≥ 18 , kidney transplant recipients (first or higher, living or deceased donor), biopsy-proven MVI ($g \geq 1$ and/or $ptc \geq 1$), C4d-negative, DSA-negative (Cohort 1) or DSA-positive (Cohort 2), informed consent.

Exclusion: C4d-positive biopsy, active TCMR $\geq IA$, infection or malignancy, multi-organ transplant, prior anti-CD38 therapy, pregnancy, breastfeeding.

UNIVERZITNÁ NEMOCNICA MARTIN
[name]
TRANSPLANTAČNO-NEFROLOGICKÉ ODDELENIE
TRANSPLANT-NEPHROLOGY DEPARTMENT

Timeline

Start: March 2026 | Primary completion: March 2027 | Study completion: September 2027

Locations

University Hospital Martin, Slovakia

Principal Investigator

[name], PhD – Transplant Nephrology Unit

Keywords

Kidney transplantation, MVI, daratumumab, dd-cfDNA, DSA, plasma cell therapy, C4d-negative rejection

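### A single published block size of 4 in an open-label 1:1 trial with one listed hospital lets staff deduce, on average, one third of allocations in advance

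*Protocol*

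**What the plan says.** Under Study Design, the protocol gives the randomisation method as "Block randomization (block size = 4) using MedCalc software", the ratio as "Allocation: Randomized (1:1 ratio" and the blinding as "Masking: Open-label (pathology and laboratory assessments blinded". The Locations section lists only "University Hospital Martin, Slovakia". The arms are subcutaneous injections or no study drug, so each past assignment is evident to local staff.

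The number randomised is less clear. The enrolment line reads "Estimated Enrollment: 80 participants (40 per cohort". The Brief Summary says "Participants with biopsy-proven MVI will be randomized to receive either daratumumab or observation with standard monitoring", and the inclusion criteria admit "DSA-negative (Cohort 1) or DSA-positive (Cohort 2". Arm A, however, is described for DSA-negative patients only: "Participants with MVI, C4d-negative, and DSA-negative will undergo observation with standard monitoring". Either 80 or 40 patients may therefore be randomised. The protocol does not mention stratification by cohort, varying block sizes, or withholding the block size from enrolling staff.

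**The concern.** With a known block size, each block can be counted down. Once one arm has used its two places, the rest of the block is known. The deduction needs only past open-label assignments and the block size, so sealed or central assignment does not stop it.

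Staff who know the next arm could, knowingly or not, bring forward, delay or pass over a candidate. If that choice follows a factor that predicts the 12-month g + ptc score, the arms differ at entry and the treatment comparison is biased. Blinded reading protects how the outcome is assessed, not who enters or when. Steering on an unmeasured factor cannot be adjusted away afterwards.

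This is not a detail left to a statistical analysis plan, because the protocol itself fixes and discloses the block size.

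**Working it through.** **Inputs from the protocol:** block size 4, ratio 1:1 (two places per arm in each block), open-label treatment, one listed hospital, 80 patients or 40 per cohort. The protocol states no predictability figure, so there is none to reproduce.

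**Share certain in advance.** There are C(4,2) = 6 equally likely orders.

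- AABB and BBAA: the last two assignments are certain.
- ABAB, ABBA, BAAB and BABA: only the last is certain.
- Mean per block = (2×2 + 4×1)/6 = 8/6 = 1.333, and 1.333/4 = 33.3%.
- By position, the chance of certainty is 0, 0, 1/3, 1.

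**Best guess (the arm with more places left).** The chance of being right by position is 1/2, 2/3, 2/3, 1. The mean is 17/24 = 70.8%.

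**Counts.** Each block has one certain assignment, plus a second with probability 1/3.

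- 80 patients, 20 blocks: 20 + Binomial(20, 1/3); mean 26.7, 95% range 23 to 31.
- 40 patients, 10 blocks: 10 + Binomial(10, 1/3); mean 13.3, 95% range 11 to 16.

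The share is the same for one pooled list or one list per cohort, provided the tracker follows the list actually in use and knows where blocks start.

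**Varying block sizes.** Each list was tracked by exact updating of the possible block states, with the set of sizes assumed known to the guesser (4,000 simulated lists; n = 80 as two lists of 40).

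| Blocks | Certain, n = 80 | Certain, n = 40 | Best guess correct |
|---|---|---|---|
| Fixed 4 | 33.35% | 33.3% | 70.8% to 70.9% |
| Random 4/6/8 | 2.41% (1.9 patients) | 2.43% (1.0 patient) | 67.6% |

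A separate run on a single list of 80 (2,000 lists) gave 2.2% certain and 67.8% for 4/6/8.

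**Illustration of possible bias.** This rests on an assumption: staff steer on an unmeasured factor by d SD. The protocol gives no value, so d = 0.10, 0.25 and 0.50 are shown. Two-way steering applies +d when one arm is expected and −d when the other is; one-way steering applies d toward one arm only. For fixed blocks of 4:

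- Two-way, certain allocations only: 2d × 1/3; at d = 0.25, 0.167 SD.
- Two-way, every best guess: 2d × (0 + 1/3 + 1/3 + 1)/4 = 2d × 0.4167; at d = 0.25, 0.208 SD.
- One-way: half of each, 0.083 and 0.104 SD.

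Type I error (%) of a t test at nominal two-sided 5%, 40,000 data sets per cell, for d = 0.10 / 0.25 / 0.50:

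| Design | Two-way, certain | Two-way, best guess | One-way, certain | One-way, best guess |
|---|---|---|---|---|
| n = 80, fixed 4 | 6.2 / 11.1 / 30.1 | 6.5 / 14.5 / 41.2 | 5.4 / 6.7 / 11.3 | 5.4 / 7.3 / 14.9 |
| n = 40, fixed 4 | 5.4 / 7.8 / 16.6 | 5.7 / 9.5 / 22.5 | 5.2 / 5.8 / 8.1 | 5.1 / 6.2 / 9.5 |
| n = 80, 4/6/8 | 5.0 / 5.1 / 5.3 | 6.0 / 11.8 / 30.8 | 5.0 / 4.9 / 5.1 | 5.2 / 6.7 / 11.7 |

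With no steering the test gave 4.8% to 5.2%.

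**Baseline adjustment** (fixed 4, n = 80, best-guess steering, d = 0.25, baseline-outcome correlation assumed 0.5, 6,000 runs). When steering is on the measured baseline score, the adjusted bias is −0.003 SD (two-way) and −0.002 SD (one-way). When it is on an unmeasured factor, the adjusted bias stays at 0.208 and 0.105 SD, with type I error 17.6% and 8.3%.

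**The case against.** The strongest reply is that the harm does not come from the document. Every type I error figure depends on an assumed d, applied at each certain or best-guess allocation. That requires several candidates to choose among or defer, and the protocol gives no recruitment rate. The main entry criteria are biopsy and laboratory findings, which limit discretion, although consent and the infection exclusion leave some. This stands: the grid shows what could happen, and only the predictability figures follow from the design.

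Second, varying blocks barely help against a best guesser. At n = 80 with two-way steering, type I error falls only from 14.5% to 11.8% at d = 0.25, and from 41.2% to 30.8% at d = 0.50. This also stands and limits the claim. The benefit is the removal of certainty.

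Third, the tracker must know where blocks start and whether there is one list or two. That is a real condition. With one hospital and 40 to 80 patients it is not hard to meet, but the protocol does not settle the list structure.

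Fourth, baseline adjustment removes steering on measured histology only if the analysis adjusts. The protocol names only a change in score. At correlation 0.5 with equal SDs, an unadjusted change score carrying a 0.208 SD baseline shift leaves (0.5 − 1) × 0.208 = −0.104 SD of bias. This widens the concern.

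**Conclusion.** The concern holds. One third of allocations are certain in advance to staff who know the block size, follow the list and know where blocks start: 26.7 of 80 on average, or 13.3 of 40. This is exact and follows from the protocol's own design. Whether bias would result is unknown. The document neither names nor rules out an unmeasured factor on which staff could select, and the bias and type I error figures rest on assumed steering. The flaw is avoidable and worth correcting before enrolment, but not fatal to the trial.

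**What to change.** Before the first patient (the Timeline gives March 2026), replace the fixed size with randomly varying permuted blocks, for example 4, 6 and 8. State in the protocol only that block sizes vary, and keep the sizes in a document that enrolling staff do not see. Reconcile the Arm A description with the Brief Summary and eligibility text so that it is clear whether both DSA cohorts are randomised; if they are, generate a separate list within each.

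The cost is regenerating the list; no patients are added. The drawback is a slight arm imbalance when the last block is incomplete. In 4,000 simulated lists with 4/6/8, the mean difference was 0.9 patients in 80 (95th percentile 2, largest 6) or 0.6 in 40 (95th percentile 2, largest 4). With fixed blocks of 4 it is 0 if enrolment ends on a complete block, and up to 2 per list if it stops mid-block.

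### Arm A limits observation to DSA-negative participants although a DSA-positive cohort is enrolled and described as randomised, so as written no DSA-positive patient can be a control

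*Protocol*

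**What the plan says.** The Protocol describes who is randomised, and to what, in several places.

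- Brief Summary: "Participants with biopsy-proven MVI will be randomized to receive either daratumumab or observation with standard monitoring". The summary restricts entry to C4d-negative biopsies but sets no DSA limit.
- Eligibility Criteria, Inclusion: "C4d-negative, DSA-negative (Cohort 1) or DSA-positive (Cohort 2), informed consent". DSA-positive patients are therefore enrolled. The title likewise covers recipients with and without DSA.
- Study Design: 1:1 randomised allocation, "Block randomization (block size = 4) using MedCalc software", and 80 participants at 40 per cohort. None of these lines mentions DSA status.
- Arms and Interventions, Arm A: "Participants with MVI, C4d-negative, and DSA-negative will undergo observation with standard monitoring".
- Arms and Interventions, Arm B: the daratumumab course, "plus standard monitoring of DSA and dd-cfDNA every 3 months", with no DSA limit.
- Arms and Interventions, Control Group: "Biopsy-negative, DSA-negative, dd-cfDNA-negative patients matched for time post-transplant and donor type".

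**The concern.** The Arm A sentence says who is observed, and it excludes DSA-positive patients. The Brief Summary, read together with the inclusion of Cohort 2, says that DSA-positive patients are randomised between daratumumab and observation. Someone allocating a DSA-positive patient gets two different answers from the same document.

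The stake is the comparator for Cohort 2. If the Arm A sentence is followed, every DSA-positive participant is in Arm B or in no arm. The Control Group cannot fill the gap, because its members have neither MVI nor DSA. A statistical analysis plan cannot repair this later, since no model supplies a comparator for patients who were never allocated to one.

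**Working it through.** **1. Can one rule satisfy all the statements?**

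| Place in Protocol | May a DSA-positive patient be assigned to observation? |
|---|---|
| Title | Implied yes (both DSA groups are studied in a randomised trial) |
| Brief Summary with Inclusion criteria | Yes |
| Study Design, 1:1 allocation | Implied yes (one ratio for the whole study) |
| Arm A | No |
| Arm B | Does not say |
| Control Group | Not applicable (DSA-negative, no MVI) |

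No single rule fits both the second and the fourth row.

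**2. The stated enrolment.** The line reads "Estimated Enrollment: 80 participants (40 per cohort". With two DSA cohorts, 2 × 40 = 80, which is consistent. The document gives no alpha, power, effect size or SD, so nothing further about the 80 can be reproduced.

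**3. Counts if the Arm A sentence is followed, with cohort meaning DSA cohort.** Take 40 DSA-negative and 40 DSA-positive patients, and let *a* be the number of DSA-negative patients observed. Then Arm A = *a*, Arm B = 80 − *a*, and the DSA-positive share of Arm B = 40/(80 − *a*). The share in Arm A is always 0.

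| Example | Arm A vs Arm B | DSA-positive in A | DSA-positive share of B | Arm-by-DSA cells filled |
|---|---|---|---|---|
| *a* = 20: Cohort 1 split 1:1, Cohort 2 all in B | 20 vs 60 | 0 | 40/60 = 67% | 3 of 4 |
| *a* = 40: arm sizes kept equal | 40 vs 40 | 0 | 40/40 = 100% | 2 of 4 |
| Both cohorts randomised, for comparison | 40 vs 40 | 20 | 20/40 = 50% | 4 of 4 |

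Other values of *a* are possible, but all leave the DSA-positive observation cell empty.

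**4. What can be estimated.** A separate treatment effect in each cohort needs four parameters: intercept, arm, DSA and arm-by-DSA. The design matrix has rank 3 in the first example, 2 in the second and 4 when both cohorts are randomised. In the first example the Cohort 1 comparison (20 vs 20) stays valid. In the second, no cohort has a randomised comparison.

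**5. Pooled comparison.** The Protocol does not say that one is planned. If the arms were compared without regard to DSA status, the bias would be the share in step 3 times *d*, the DSA-related difference in 12-month change. That is 0.67*d* in the first example and 1.00*d* in the second. The document does not give *d*.

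**6. If cohort in the enrolment line means arm.** The arms are then 40 vs 40 and the number of DSA-positive patients is not given. At an assumed 10, 20 or 30, all in Arm B, the share is 25%, 50% or 75%. The number observed is still 0.

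**7. Price of giving up randomisation in Cohort 2.** Assume a two-sample comparison of means with equal variances, two-sided 5% and 80% power. With *n* per arm the noncentrality is δ√(*n*/2) on 2*n* − 2 degrees of freedom.
- *n* = 40: δ = 0.634 SD (0.634 × √20 = 2.84, 78 df).
- *n* = 20: δ = 0.909 SD (0.909 × √10 = 2.87, 38 df).
- *n* = 20 at δ = 0.634 SD: power 0.498, against 0.800 with *n* = 40.

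These are approximations for a Banff g + ptc score, which takes few values. The 40 vs 40 figures apply only if both cohorts are analysed together.

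**The case against.** The strongest reply is that the document as a whole points one way. The title, the Brief Summary, the study-wide 1:1 ratio and the two-cohort eligibility rule all suggest that both cohorts are randomised. Only the DSA restriction in Arm A points the other way, and it looks like a drafting slip. Each literal example also breaks another explicit line, so neither is a design the whole text supports. This has weight: a slip is a plausible explanation, and if the Brief Summary governs, the consequences disappear. But the document sets no order of precedence, and the Arms section is the more specific text. If Arm A was meant to describe Cohort 1 only, the document gives no arm-level description of how Cohort 2 is allocated. A correction is needed on any of these readings.

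Three narrower points stand as limits on the figures.
- A before-after description of Cohort 2 would remain possible without observed patients. What is lost is any controlled comparison.
- The pooled bias matters only if an unadjusted pooled analysis is done, and analysis choices may properly sit in the statistical analysis plan.
- The rise from 0.63 to 0.91 SD assumes that the cohorts would have been pooled. If each cohort is analysed separately, Cohort 1 is 20 vs 20 either way, and the loss is the Cohort 2 comparison itself.

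**Conclusion.** The concern holds, and the text must be corrected before the trial starts. The core result needs no assumption beyond the Arm A sentence itself: applied as written, it places 0 DSA-positive patients in observation. With 40 per DSA cohort, that leaves half of the planned 80 without a randomised comparator and breaks either the 1:1 ratio or the randomisation itself. Confidence is high that the passages conflict. How the trial would actually be run is unknown, so every count beyond the zero depends on the literal rule and on the reading of cohort.

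**What to change.** Reconcile the Arm A definition with the Brief Summary, title, eligibility criteria and allocation line before the first patient is allocated. Who is observed and who is treated is for the sponsor to decide. The document should then state one of two things.

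- **Both cohorts are randomised.** Say that Cohort 1 and Cohort 2 each enter both arms. This wording alone removes the contradiction. Preferably, also apply the stated blocks of 4 within each DSA cohort: 40/4 = 10 full blocks, giving 20 per arm per cohort. Cost: protocol wording and one randomisation list per cohort before the March 2026 start, with no extra patients or procedures.
- **Cohort 2 is not randomised to observation.** Declare it a separate non-randomised cohort, and restate the title question and the randomised sample as 40 (20 per arm). Cost: the randomised answer for DSA-positive recipients is given up. Compared with a pooled 40 vs 40 analysis, the detectable difference rises from about 0.63 to 0.91 SD under the assumptions stated above.

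On either route, say whether cohort in the enrolment line means DSA cohort or arm.

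### The only adverse-event outcome counts events attributed to daratumumab, so the observation arm scores zero by definition and the trial has no randomised comparison of non-fatal harm

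*Protocol*

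**What the plan says.** Under Outcome Measures, the fifth secondary outcome is "Adverse events related to daratumumab". No other listed outcome covers adverse events, serious adverse events or infections. The sixth, "Patient and graft survival at 12 months", captures death and graft loss, and the first captures change in eGFR.

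The Brief Summary describes the comparison: "Participants with biopsy-proven MVI will be randomized to receive either daratumumab or observation with standard monitoring". In Arms and Interventions, Arm A participants "will undergo observation with standard monitoring". No placebo is described. Study Design gives "Masking: Open-label (pathology and laboratory assessments blinded" and "Estimated Enrollment: 80 participants (40 per cohort".

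The scheduled monitoring is the same in both arms. For Arm A, "DSA and dd-cfDNA will be measured every 3 months for 12 months"; Arm B receives three monthly doses "plus standard monitoring of DSA and dd-cfDNA every 3 months". Neither entry mentions adverse-event enquiries.

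**The concern.** A randomised untreated arm allows the trial to separate harm caused by the drug from harm that transplant recipients suffer anyway. Outcome 5 gives that up, because an event counts only if someone attributes it to daratumumab. This is impossible in Arm A and a matter of unblinded judgement in Arm B.

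The Arm B figure is therefore the true event rate multiplied by the attributed share, and the two factors cannot be separated. A generous attribution habit would suggest harm where there is none, and a sparing one would conceal real harm. If daratumumab improves the microvascular inflammation score, the reader will want to weigh that against non-fatal harm, and the listed outcomes supply no randomised estimate of it.

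**Working it through.** **What follows from the wording alone.** No assumed rate is needed for these three steps.

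1. Outcome 5 requires a relation to daratumumab (Outcome Measures).
2. Arm A receives no daratumumab (Brief Summary; Arms and Interventions). Its count is 0 by definition.
3. Causality judgement is not among the blinded assessments (Study Design). The Arm B count depends on assessors who know the allocation.

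**How far the reading can mislead.** The protocol gives no event rates and no figure to reproduce, so the rates and shares below are assumptions. Infection is used as the example. Write *p* for the all-cause proportion infected in Arm B and *f* for the share attributed to the drug. Outcome 5 then reads *p* × *f* in Arm B and 0 in Arm A. If all 80 participants are randomised 1:1, there are 40 per arm.

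| Attributed share *f* | No excess (30% v 30%) | 20-point excess (50% v 30%) |
|---|---|---|
| 0.25 | 0.30 × 0.25 = 7.5% (3 of 40) | 0.50 × 0.25 = 12.5% (5 of 40) |
| 0.50 | 0.30 × 0.50 = 15.0% (6 of 40) | 0.50 × 0.50 = 25.0% (10 of 40) |
| 0.75 | 0.30 × 0.75 = 22.5% (9 of 40) | 0.50 × 0.75 = 37.5% (15 of 40) |

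The two ranges, 7.5–22.5% and 12.5–37.5%, overlap from 12.5% to 22.5%, that is 5 to 9 of 40. A reading of 15% (6 of 40) arises from 0.30 × 0.50, with no excess, and equally from 0.50 × 0.30, with a 20-point excess.

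**If someone compared the arms anyway.** The protocol names no test for this outcome, so this is only a warning about misuse. With 40 per arm, 6 events against 0 is the smallest count that gives a two-sided Fisher p below 0.05. With identical 30% risk in both arms and half of Arm B events attributed, 6 or more occur with probability 0.57.

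**What an all-cause outcome would give.** For 50% against 30%, the 95% half-width of the risk difference is 1.96 × √(0.50 × 0.50/*n* + 0.30 × 0.70/*n*) = 1.96 × √(0.46/*n*).

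- *n* = 40 per arm: 1.96 × √0.0115 = 0.210, so the interval is −0.01 to 0.41.
- *n* = 20 per arm: 1.96 × √0.023 = 0.297, so the interval is −0.10 to 0.50.

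The second line would apply to one DSA cohort of 40 if it were split 1:1. The protocol does not firmly establish that split, because it describes Arm A as DSA-negative only.

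**The case against.** The strongest reply is that the protocol is a short synopsis in which every outcome is a brief phrase. Outcome 5 might be shorthand for the types of event known to occur with the drug, and these could be counted in both arms. All-cause tabulations by arm are usual SAP content, and the SAP is not at hand. The protocol does not say that Arm A events go unrecorded, plans no between-arm test and makes no comparative safety claim. The illustration rests wholly on assumed rates. Even after the change the estimate would be imprecise, with about 45% power at 40 per arm for 50% against 30%.

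Much of this stands and limits the claim. The rates are illustrative, the gain in precision is modest, and Arm A events may well be recorded.

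The alternative reading does not stand: it strains the wording, and nothing else in the protocol supports it. Nor is this only a detail left to the SAP. The restriction to drug-related events is written into the protocol's outcome definition, and an unseen SAP cannot be assumed to lift it. A count of drug-related events is a legitimate summary; the weakness is that it is the only adverse-event outcome.

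**Conclusion.** The concern holds. Followed as written, outcome 5 gives zero in Arm A and an unblinded, attribution-dependent count in Arm B, so the listed outcomes contain no randomised comparison of non-fatal adverse events. That conclusion needs only the outcome wording and the arm descriptions.

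The size depends on the assumptions of 30% and 50% infection rates and 25–75% attribution. Under them, one observed figure can be consistent with anything from no excess to a 20-point excess.

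The primary outcome is unaffected, and survival and eGFR change remain comparable between arms. The change should be made before enrolment starts, because Arm A events not sought prospectively in the same way cannot be reliably recovered later.

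**What to change.** Reword secondary outcome 5 along these lines:

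> All adverse events and serious adverse events, regardless of relatedness, from randomisation to month 12, ascertained on the same schedule and in the same way in both randomised arms and reported by arm, with infections shown separately.

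Keep relatedness as a descriptive attribute in Arm B. Report the between-arm difference with its 95% confidence interval as an estimate, not as a powered test.

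Equal ascertainment needs some care. Both arms have 3-monthly monitoring, to which a structured adverse-event enquiry can be attached. Monthly dosing implies additional contacts in Arm B. If adverse events are also sought at those contacts, Arm A needs matching enquiries in the same months, for example by telephone.

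The cost is one line of outcome wording and modest extra data collection in Arm A. Treatment and sample size do not change.
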